7.3 Confirmation of therapy success

Following completion of therapy, patients admitted to labor and delivery will have 1 additional swab. The swabs can be collected by the provider during performing normal labor exam or it can be self-collected by the patient. This swab will be sent to the lab for another gram stain. However, results will not be used for clinical decision guidance. It will be used for analysis later.

7.4 Clinical care: The care of patients in the remaining antepartum period, intrapartum period, including the method of induction or augmentation of labor will be according to standard of care at the participating site, and per the managing clinical team. After a subject who meets inclusion criteria agrees to participation in our study, the obstetric team will contact one of the investigators. Signed informed consent will be obtained by the PI, Co-Investigators or study coordinators. The total participation time in the study will be considered terminated at 6 weeks postpartum. No additional antepartum or postpartum will be required for the study, only routine visits will be recommended.

7.5 Data collection: The data collected will be kept on a password-secured Ohio State Wexner Medical Center (OSUWMC) computer. An encrypted USB flash drive will be used to transfer data. The data will be linked to the patient by patient's MRN number. This identifier is needed to access and analyze demographic data. During analysis of the data, all identifiers will be deleted.

7.6 Informed consent. Under the direction of the PI, trained research staff will be available 24/7 to screen and consent patients according to study protocol. Patients will be enrolled in clinic at or after 34 weeks gestation.

A written informed consent will be obtained to screen patients for BV via 3 self-collected vaginal swabs and testing for Amsel criteria and gram stain, in-addition to storage for later microbiome analysis. Randomization and treatment will then follow if positive by Amsel criteria. Vaginal swab for Gram stain will also be collected at time of admission to L&D for Labor for later analysis, and not for clinical decision-making. Full disclosure of the nature and potential risks of participating in the trial are to be made. Women who are not fluent in English will be enrolled by a person fluent in their language. Both verbal and written informed consent and authorization will be obtained in that language; if this is not possible, the patient will not be included. A copy of the signed consent form will be provided to the patient.

7.7 Screening and consent procedures. Under the direction of the study team members, we will enroll patients in clinic at or after 34 weeks gestation.

Medical records of all potential patients will be reviewed and those who satisfy inclusion and exclusion criteria will be approached for informed consent. If the potential subjects are not patients of the investigators then the permission of the treating provider will be obtained before approaching the patients to invite them to participate in research.

Written consent will be obtained by direct person-to-person contact. The principal investigator, co-Investigator, or study coordinators will be responsible for the informed consent. Non-English speaking subjects are anticipated to be part of the study population and informed consent will be provided in their primary language. The data collected will not be used for clinical management. Subjects will be reassured that participation in the study is voluntary and will not interfere with diagnosis or treatment of her condition or management of her labor. The subjects will receive the same care and expertise as any other patient treated in our unit.

Informed consent will be obtained to screen for BV, and if BV positive, participate in the study. A screening log will be used to track all patients approached for the study, according to local guidelines.

7.8 Randomization and Masking: After obtaining informed consent, women with BV will be randomized to either control or study group according to a randomization sequence that is computer generated and maintained by the investigational drug pharmacy. A study enrollment log with a study ID number, subject name and medical record number, will be used to track enrolled patients. The investigational pharmacy at OSUMC will be notified after randomization and study drugs or placebos will be sent as dictated by patient's randomization group.

7.9 Drug Administration and Dispensation. Once a subject is consented randomization will be performed by the OSUWMC's investigational drug pharmacy (IDS). The appropriate study drug according to the group assignment will then be dispensed by OSUWMC's investigational drug services (IDS) pharmacy as well. Patients will receive 7 days of metronidazole 500 BID oral or similarly appearing placebo. The 14 pills will be provided in a container. The IDS pharmacy will dispense the drugs, account for dispensing and stock number. Funding provided by the department will cover the cost of the medications, and the patient's insurance company will not be billed. Subjects will be instructed to bring the container to clinic next visit or on admission to labor and delivery to count remaining pills and assess adherence.

The subject will be included in the analysis by intent-to-treat.

7.10 Baseline Procedures. Routine Ante, intra- and postpartum care will be provided to patients according to the local standard of care. Patients' clinical providers who will be blinded to the study interventions. Trained and experienced research staff (also blinded to group assignment) will be responsible for screening patients in clinic for eligibility and for all research data abstraction. All data will be de-identified after collection and tracked only with a study ID number.

The PI and co-PI will review and validate the diagnosis for all patients identified to have the primary composite outcome, applying current CDC and other standard criteria. These reviews

will be conducted masked to treatment group. If there is uncertainty, a second investigator will review the chart, discuss with the PI as needed, and make a final determination regarding the outcome. Maternal and neonatal outcomes will be assessed in the hospital following delivery (on an ongoing basis until discharge) and at the routinely scheduled postpartum follow-up visits up to 6 weeks postpartum.

7.11. Study visits / Follow-up. Part of the standard of care, all postpartum patients are followed after delivery to assess any postpartum complications. Before the subject leaves the hospital, patients are usually given their follow up appointment. This will be documented in the datasheet, in order to ascertain follow up. Patients will be educated about the signs and symptoms of infection and other study outcomes and encouraged to call the study research team with any concerns. In addition, records of visits (to any hospital clinic or ER) prior to the routine postpartum visit will be obtained and reviewed to ascertain study outcomes (treating providers may also be called if clarifications are needed). Finally, if patient does not present to routine postpartum care, a research staff will call all patients at 6 weeks postpartum to inquire about occurrence of study outcomes. Newborn outcomes will be ascertained through initial discharge from hospital or up to 90 days or death, whichever occurs first. Readmissions and related diagnoses for infants will also be ascertained through medical records.

7.12. Withdrawals. Patients who withdraw from the study after randomization will be followed up to ascertain outcomes. Outcomes ascertained will be reported in intent to treat fashion.

7.13. Primary Outcome #1: Composite of chorioamnionitis, postpartum endometritis, SSI, wound infection, or other post Cesarean infections (occurring within 6 weeks after delivery) defined as follows. These outcomes will be defined and assessed by trained research staff and reviewed and validated by the investigators, all blinded to group assignment.

1) Chorioamnionitis: this will be diagnosed if patient develops: Fever (defined as either 2 readings of $\geq 38.0^{\circ}\text{C} / 100.4^{\circ}\text{F}$ 30 minutes apart or one reading $\geq 39.0^{\circ}\text{C} / 102.2^{\circ}\text{F}$) in the absence of any cause for fever PLUS one of the following: 1) fetal tachycardia (>160 for 30 minutes or longer), 2) Leukocytosis (> 15000 in absence of corticosteroids), 3) Purulent discharge from cervical os, 4) biochemical or microbiological changes of the amniotic fluid (positive gram stain, positive culture, low glucose, high WBC).(1)

2) Endometritis: If the patient develops two of the following: 1) Oral body temperature of 101°F at any time, or a temperature of 100.4°F 24 hours after delivery, 2) maternal tachycardia that parallels the temperature, 3) Uterine tenderness, 4) purulent vaginal discharge, or 5) Associated findings with advanced endometritis (dynamic ileus, pelvic peritonitis, pelvic abscess, bowel obstruction, necrosis of the lower uterine segment) (1)

3) SSI: We will also be following the criteria set by the CDC's National Healthcare Safety Network (formerly the National Nosocomial Infection Surveillance System) for hospital-acquired SSI:

A **superficial incisional SSI** must meet the following criteria:

Date of event for infection occurs within 30 days after the operative procedure (where day 1 = the procedure date) **AND** involves only skin and subcutaneous tissue of the incision **AND** patient has at least one of the following:

- a) Purulent drainage from the superficial incision.
- b) Organisms identified from an aseptically-obtained specimen from the superficial incision or subcutaneous tissue by a culture or non-culture based microbiologic testing method which is performed for purposes of clinical diagnosis or treatment (e.g., not Active Surveillance Culture/Testing (ASC/AST)).
- c) Superficial incision that is deliberately opened by a surgeon, attending physician or other designee and culture or non-culture based testing is not performed. **AND** Patient has at least one of the following signs or symptoms:
 - a. pain or tenderness;
 - b. localized swelling;
 - c. erythema;
 - d. or heat.
- d. Diagnosis of a superficial incisional SSI by the surgeon or attending physician or other designee.

A **deep incisional (or wound) SSI** must meet the following criteria:

The date of event for infection occurs within 30 after the operative procedure (where day 1 = the procedure date) **AND** involves deep soft tissues of the incision (e.g., fascial and muscle layers) **AND** patient has at least one of the following:

- a) Purulent drainage from the deep incision.
- b) A deep incision that spontaneously dehisces, or is deliberately opened or aspirated by a surgeon, attending physician or other designee and organism is identified by a culture or non-culture based microbiologic testing method which is performed for purposes of clinical diagnosis or treatment (e.g., not Active Surveillance Culture/Testing (ASC/AST) or culture or non-culture based microbiologic testing method is not performed **AND** patient has at least one of the following signs or symptoms:
 - a. Fever ($>38^{\circ}\text{C}$); localized pain or tenderness.
 - b. A culture or non-culture based test that has a negative finding does not meet this criterion.
- c) An abscess or other evidence of infection involving the deep incision that is detected on gross anatomical or histopathologic exam, or imaging test.

An **organ/space SSI (e.g. endometritis or abscess)** involves any part of the body, excluding the skin incision, fascia, or muscle layers, that is opened or manipulated during the operative procedure. An **organ/space SSI (endometritis or abscess)** must meet one of the following criteria:

Infection occurs within 30 days after the operative procedure **AND** infection involves any part of the body, excluding the skin incision, fascia, or muscle layers, that is opened or manipulated during the operative procedure **AND** patient has at least one of the following:

- a) Purulent drainage from a drain that is placed through a stab wound into the organ/space;
- b) Organisms isolated from an aseptically obtained culture of fluid or tissue in the organ/space;

- c) An abscess or other evidence of infection involving the organ/space that is found on direct examination, during reoperation, or by histopathologic or radiologic examination;
- d) Diagnosis of an organ/space SSI by a surgeon or attending physician.

4) Wound infection: Presence of either superficial or deep incisional SSI described as cellulitis/erythema and induration around the incision or purulent discharge from the incision site, with or without fever, such as necrotizing fasciitis (diagnosed based on necrotizing wound infection). Wound hematoma, seroma, or breakdown alone in the absence of the above signs does not constitute infection.

5) Other infections: Pelvic septic thrombosis (diagnosis based on persisting signs of endometritis with or without radiological confirmation), abdominal or pelvic abscess based on radiological diagnosis.

- Primary outcome #2 Validation of NAAT in diagnoses and treatment of BV in pregnant women in the third trimester

7.14 Secondary Outcomes

Maternal secondary outcomes:

- Individual infections: chorioamnionitis, endometritis, wound infection (including necrotizing fasciitis), other infections including abscess, septic thrombosis, pneumonia, pyelonephritis and breast infection
- Maternal Death
- Puerperal fever: Temperature > 100.4 F at least twice 30 minutes apart, or once with the use of antipyretic, or ≥ 101 F once. This will be analyzed for intrapartum and postpartum fever.
- Use of resources: Hospital stay, postpartum clinic or emergency room visit within 4 weeks of delivery, need for imaging or other invasive procedures, postpartum antibiotic use.
- Adverse events: Allergic reactions (anaphylaxis, angioedema, skin rashes including Stevens Johnson and Toxic Epidermal necrolysis), GI symptoms (nausea, vomiting, diarrhea, constipation, ileus, etc)

Neonatal secondary outcomes:

- Suspected sepsis (need for sepsis work-up): Presence of clinical signs/symptoms (hypothermia, fever, irritability, poor feeding, hypotonia, etc) causing the clinician to perform a sepsis work-up (blood, urine and/or cerebrospinal fluid, or chest X-ray), within 7 days of delivery- excludes routine work-up solely for positive maternal GBS status.
- Confirmed sepsis: Findings indicating positive cultures of blood, cerebrospinal fluid or urine obtained by catheterization or suprapubic aspiration, or cardiovascular collapse, or an unequivocal X-ray confirming infection in a clinically septic neonate, within 7 days of delivery.
- NICU admission and duration

- Neonatal morbidities:** Respiratory distress syndrome (RDS), necrotizing enterocolitis (NEC), periventricular leucomalacia (PVL), intraventricular hemorrhage (IVH), and BPD. RDS is presence of any one of i) oxygen requirement at 6-24 hours of life in a preterm infant, ii) abnormal chest radiograph consistent with RDS, or iii) need for surfactant; NEC is based on the clinical diagnosis of the neonatologist supported by findings on radiological imaging, surgical intervention and/or autopsy; IVH and PVL are diagnosed by an attending neonatologist based on clinical indications leading to a confirmatory ultrasound interpreted by a certified radiologist; BPD (or chronic lung disease) is defined as infant oxygen requirement at 28 days, at 36 weeks post-conceptual age or at time of hospital discharge

8. SOURCES OF RESEARCH MATERIAL: Electronic Medical chart/records.

9. POTENTIAL RISKS:

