Neither the patient nor provider will be aware of treatment assignment. No significant adverse effects are expected with the use of antibiotics in the study population. As with any other instance in which antibiotics are administered, there is a chance of an allergic or other adverse reaction. The patient will receive standard inpatient monitoring during the labor course and in the postpartum period, and so any immediate adverse reaction can be promptly detected. The study period will be November 2020 to September 2022. The number of subjects studied will be 482 patients. If a patient wishes to withdraw from study after randomization and receipt of study medications, no additional interventions will be performed, but we will collect study outcomes as this is intent to treat study and patients' outcomes will be analyzed in the group they were assigned to.

5. INCLUSION CRITERIA:

- Pregnant women 18 to ≤50 years with the ability to give informed consent.
- Patients expected to have a vaginal delivery with no obstetric contraindication for vaginal delivery at time of screening.
- Gestational age ≥ 34 weeks

6. EXCLUSION CRITERIA:

- Plan for elective cesarean delivery
- Allergy or contraindications to metronidazole
- Receipt of metronidazole or clindamycin on admission for delivery for other indications.
- Hemodialysis
- Severe liver dysfunction
- Patient reports BV to nurse or clinician provider at current clinic visit or has been treated for BV within the past 3 months.

7. STUDY PROCEDURES:

7.1 Randomization and enrollment in clinic at or after 34 weeks: After obtaining informed consent, patients with a plan for vaginal delivery will be screened for BV by self-collecting 2 vaginal swabs for Gram stain, and Amsel criteria. A 3rd swab will be collected and stored at -80C for future microbiome analysis at the end of the study. The 3rd swab for future microbiome analysis is associated only with this study. When all study is complete, we will run the analysis to see if there is an association between microbiome and peripartum infections. The reason for storing the specimens and running them at the end is to decrease the cost. Patients with positive Amsel criteria will be eligible for randomization. Randomization and providing the patient with medications will be done at the same visit.

7.2 Clinical diagnosis of BV:

Amsel criteria are:

- Homogenous thin grayish-whitish discharge that coats vaginal mucosa
- Vaginal PH >4.5

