9.3 Risks from intervention

Most common adverse effects associated with metronidazole use are gastrointestinal, nausea, vomiting, anorexia, cramping, constipation and diarrhea, others adverse effects include headache. Metronidazole is categorized as pregnancy category B by FDA. GI adverse effects are common. Nausea affects about 12% of patients, diarrhea and abdominal pain affects 4%. Headache affects 18 % of patients. Hypersensitivity affects 5%. However, severe allergic reactions are very rare.

There are rare risks of serious peripheral and central nervous system issues, hematopoiesis, and cardiovascular and renal adverse reactions. Additionally, there are risks of drug interactions, including with alcohol. There are risk of fungal overgrowth/yeast infection and the risk of experiencing an unpleasant metallic taste. Metronidazole crosses the placental barrier. Though there is no evidence of harm to the fetus, it is present in breast milk for up to 24 hours after treatment ends.

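### The adverse-event outcome in section 7.14 names only allergic and GI events, so headache, yeast infection and the serious non-allergic reactions named in section 9.3 have no planned between-arm comparison

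*Combined protocol and SAP*

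**What the plan says.** **Section 7.14 (maternal secondary outcomes)** gives the safety outcome as "Adverse events: Allergic reactions (anaphylaxis, angioedema, skin rashes including Stevens Johnson and Toxic Epidermal necrolysis), GI symptoms (nausea, vomiting, diarrhea, constipation, ileus, etc"). There are two groups. The closing *etc* falls inside the GI bracket, so it extends the GI group only. Maternal death is a separate secondary outcome.

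**Section 9.3** names a wider set of risks. It calls GI effects the most common group, with nausea at about 12% and diarrhea and abdominal pain at 4%. It then states "Headache affects 18 % of patients" and puts hypersensitivity at 5%, adding "However, severe allergic reactions are very rare". It goes on: "There are rare risks of serious peripheral and central nervous system issues, hematopoiesis, and cardiovascular and renal adverse reactions". Yeast infection and metallic taste are also named, without rates.

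**Section 10** provides for a monitoring report that includes a summary of AEs and SAEs. It gives no categories, no method of ascertainment and no split by arm.

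**Section 13** has no separate safety analysis. It says in general terms that incidence rates will be compared between groups by chi-square or Fisher's exact test.

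**Sections 7.11 and 8** direct follow-up. Patient education, record review and the 6-week call are aimed at the study outcomes, and the stated source of research material is the electronic record.

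**The concern.** Under the standard of care described in sections 1.1 and 2.5, asymptomatic BV in pregnancy is not treated. A positive result would support giving an antibiotic to women who do not now receive one, so readers will want harms set against benefit, by arm.

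The 7.14 list determines which harms are defined outcomes, and through section 7.11 it also determines what staff are directed to ask about. As it stands, the planned comparison covers nausea and rash. It does not cover the adverse effect with the highest single stated rate, the serious non-allergic reactions, or yeast infection, which is of natural interest in a trial that alters vaginal flora. Yeast infection is not named in the 7.14 individual-infections item either.

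A blinded placebo arm is the best means of separating drug-related headache from background headache in late pregnancy. The plan does not say that it will be used for this.

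**Working it through.** **1. The two lists side by side**

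| Risk named in 9.3 | Rate in 9.3 | In the 7.14 adverse-event item? |
|---|---|---|
| Headache | 18% | No |
| Nausea | about 12% | Yes |
| Hypersensitivity | 5% | Yes, as allergic reactions |
| Diarrhea and abdominal pain | 4% | Yes, as GI symptoms |
| Severe allergic reactions | very rare, no figure | Yes |
| Serious nervous system, hematopoietic, cardiovascular, renal reactions | rare, no figure | No |
| Yeast infection | none given | No |
| Metallic taste | none given | No |

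**2. The arm size.** Section 13 gives 241 per group for 17% against 8.5% (a 50% reduction), 80% power and alpha 0.05. With a two-sided test, pooled variance and no continuity correction:

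n = [1.960 × √(2 × 0.1275 × 0.8725) + 0.8416 × √(0.17 × 0.83 + 0.085 × 0.915)]² / 0.085² = (0.9245 + 0.3937)² / 0.007225 = 240.5, rounded up to 241.

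The plan's figure is reproduced, and nothing in this point changes it.

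**3. Expected counts among 241 women on metronidazole** (rate × 241)

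- Headache: 0.18 × 241 = 43.4
- Nausea: 0.12 × 241 = 28.9
- Hypersensitivity: 0.05 × 241 = 12.1
- Diarrhea and abdominal pain: 0.04 × 241 = 9.6

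The largest single count belongs to an event outside the outcome. These are gross counts in the treated arm.

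**4. Would a headache comparison be informative?** The documents give no placebo headache rate, so a range is assumed. The excess is 241 × (0.18 − placebo rate). Power is for a two-sided 5% test with 241 per arm.

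| Assumed placebo rate | Excess cases in 241 | Power |
|---|---|---|
| 5% | 31.3 | 99.5% |
| 8% | 24.1 | 91% |
| 10% | 19.3 | 72% |
| 12% | 14.5 | 45% |
| 15% | 7.2 | 14% |

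The comparison could be informative or weak, depending on a background rate that the plan does not supply. An estimate with a confidence interval is useful in either case.

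**5. The rare serious reactions.** No rates are stated. The chance of at least one case in 241 treated women is 1 − (1 − r)^241: 21% at an assumed r = 0.1%, 70% at 0.5% and 91% at 1%. With so few expected cases these events can be listed by arm but not usefully tested.

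**The case against.** The strongest reply is that leaving an event out of a secondary-outcome list does not mean it is lost. Section 7.14 does not say that other events are excluded, the section 10 summary has no category limit, and section 13 does not restrict which incidence rates are compared. Once the pharmacy-held allocation is opened, any recorded event can be tabulated by arm. This stands as far as it goes: the gap is that no by-arm comparison is specified in advance, and the documents do not show that the events would go unrecorded.

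Several stronger readings are tempting and are not supported:

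- *All serious risks are omitted.* Anaphylaxis, angioedema, Stevens-Johnson, toxic epidermal necrolysis and maternal death are listed in 7.14. The omission concerns the nervous system, hematopoietic, cardiovascular and renal reactions.
- *The safety report is masked, so it cannot compare arms.* Section 10 does not mention masking. Section 7.10 masks the abstracting staff, but that would not prevent a final tabulation by arm.
- *Forty-three headaches are caused by treatment.* Without a placebo rate the excess is unknown, so the most that can be said is that harm could be understated.
- *Headache is the most common adverse effect.* It has the highest single stated rate, but 9.3 calls GI effects as a group the most common.
- *Section 4.2 contradicts 9.3.* It says "No significant adverse effects are expected with the use of antibiotics in the study population", but then allows for allergic or other reactions. If significant means serious, this agrees with the risks that 9.3 calls rare. The wording is loose and not a clear contradiction.

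A further objection concerns the remedy. With electronic records as the source, mild headache during a week of outpatient dosing may never be charted, so extra fields on an abstraction form would not be enough. That is correct, and the fix allows for it.

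**Conclusion.** The point holds as a gap in the planned safety comparison. The 7.14 item omits headache, yeast infection and the serious non-allergic reactions that section 9.3 itself names, and neither section 10 nor section 13 states that they will be tabulated by arm. At the plan's own figures about 43 of 241 treated women would have headache, against about 29 with nausea.

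The counts assume that the 9.3 rates apply to women treated after 34 weeks and that 241 are allocated to metronidazole. The excess over placebo cannot be derived from the documents. The primary outcome, the sample size and the efficacy inference are unaffected. The change should be made because the trial bears on whether to treat women now left untreated, and it is cheap.

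**What to change.** 1. Extend the 7.14 adverse-event item to add headache, vulvovaginal yeast infection, the serious nervous system, hematopoietic, cardiovascular and renal reactions named in 9.3, and two summary lines: any AE and any SAE. Metallic taste need not be a named outcome, since any AE would include it.
2. State in section 13 that each item will be tabulated by randomised arm, with the difference and confidence interval for the common symptoms, and that rare events will be described rather than tested.
3. Ask about the symptom items at contacts that already exist: the pill-count visit or labor admission (section 7.9), and the routine postpartum visit or 6-week call (section 7.11). Use the same questions in both arms.

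The cost is a few added questions, a little more abstraction and one more table. Sample size, treatment and the visit schedule do not change.

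### The adverse-event outcome in section 7.14 has no onset window around the 7-day course, so peripartum symptoms dilute the drug-placebo comparison of harm

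*Combined protocol and SAP*

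**What the plan says.** Section 7.14 lists adverse events among the maternal secondary outcomes: allergic reactions of several kinds and "GI symptoms (nausea, vomiting, diarrhea, constipation, ileus, etc". It gives no onset window, severity threshold or attribution rule, and sections 9.3, 10 and 13 supply none. Other outcomes do carry windows: 4 weeks from delivery for clinic and emergency visits, 7 days for neonatal sepsis, and 6 weeks for the primary composite.

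Exposure is short and falls before delivery. Section 7.9: "Patients will receive 7 days of metronidazole 500 BID oral or similarly appearing placebo". Section 7.1 has the medication handed over at the randomization visit, and enrollment opens at 34 weeks.

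Observation is long and centers on delivery. Section 7.4: "The total participation time in the study will be considered terminated at 6 weeks postpartum". Section 7.10: "Maternal and neonatal outcomes will be assessed in the hospital following delivery (on an ongoing basis until discharge", followed by routine postpartum visits to 6 weeks. On detection of reactions, section 4.2 says: "The patient will receive standard inpatient monitoring during the labor course and in the postpartum period". Section 7.4 adds no study visits, and section 8 names the electronic chart as the data source.

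In section 7.13, one of the five endometritis criteria within the primary composite reads: "Associated findings with advanced endometritis (dynamic ileus, pelvic peritonitis, pelvic abscess, bowel obstruction", with one further finding after these.

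**The concern.** Nausea, vomiting, constipation and ileus can arise from labor, cesarean delivery or infection, weeks after a woman's last study pill. Without an onset rule, such a symptom counts the same as one that began on the second day of dosing. Two consequences follow.

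- **Dilution.** Symptoms equally common in both arms pull the relative risk toward 1, reduce the absolute difference and add variance. A real gastrointestinal effect of metronidazole becomes harder to see.
- **Overlap with efficacy.** Ileus can count both toward a primary-outcome infection and as an adverse event. If treatment prevents endometritis, the adverse-event count on metronidazole falls for that reason and offsets true drug harm. This part is not symmetric between arms.

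Section 2.5 says that asymptomatic women are not currently treated. A case for treating them would need a credible tolerability comparison as well as an efficacy result.

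**Working it through.** **1. The plan's own figure.** Section 13 gives 241 per group for 17% versus 8.5%, 80% power, alpha 0.05. With pooled variance under the null, two-sided:

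n = [1.960·√(2·0.1275·0.8725) + 0.842·√(0.17·0.83 + 0.085·0.915)]² / 0.085² = (0.9245 + 0.3937)² / 0.007225 = 240.5, so 241.

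The figure reproduces and is not in dispute. The plan sets no power target for adverse events; 241 per arm is used below as the available sample.

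**2. Inputs for the illustration.**
- Nausea on metronidazole: 12%, from section 9.3, taken as the rate during dosing.
- Nausea on placebo during dosing: 5%, assumed (range 2% to 8% in step 5).
- Background b, the chance of a counted nausea event outside the dosing period, equal in both arms: assumed, 0 to 50%.

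**3. Formulas.** Counted rate in an arm with dosing-period rate p is 1 − (1−p)(1−b). The difference between arms is then (p_drug − p_placebo)(1−b). Power is Φ[(difference − 1.96·SE0)/SE1], with SE0 = √(2·p̄(1−p̄)/241) and SE1 = √{[p_d(1−p_d) + p_p(1−p_p)]/241}, where p_d and p_p are the counted rates and p̄ is their mean.

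At b=0: SE0 = 0.0254, SE1 = 0.0252; (0.070 − 0.0498)/0.0252 = 0.80; power 79%.

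At b=10%: SE0 = 0.0347, SE1 = 0.0346; (0.063 − 0.0681)/0.0346 = −0.15; power 44%.

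**4. Results, 12% versus 5%.**

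| b | Drug | Placebo | Difference (points) | Power |
|---|---|---|---|---|
| 0 | 12.0% | 5.0% | 7.0 | 79% |
| 2% | 13.8% | 6.9% | 6.9 | 70% |
| 5% | 16.4% | 9.8% | 6.7 | 58% |
| 10% | 20.8% | 14.5% | 6.3 | 44% |
| 20% | 29.6% | 24.0% | 5.6 | 28% |
| 30% | 38.4% | 33.5% | 4.9 | 20% |
| 50% | 56.0% | 52.5% | 3.5 | 12% |

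Between b=0 and b=10% the difference shrinks by a tenth, while SE0 grows from 2.5 to 3.5 points. Most of the loss at that level is added variance.

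**5. Sensitivity to the placebo rate.**

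| Placebo rate | Power, b=0 | b=10% | b=20% |
|---|---|---|---|
| 2% | 99% | 76% | 52% |
| 4% | 90% | 55% | 36% |
| 6% | 63% | 34% | 22% |
| 8% | 31% | 17% | 12% |

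The level depends heavily on the placebo rate. The downward pattern does not.

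**6. Background linked to infection.** Suppose a fraction f of primary-outcome infections carries a counted gastrointestinal symptom (assumption) and treatment halves infection as planned. Background is then 17%·f on placebo and 8.5%·f on drug.
- f=10%: drug 1 − 0.88·0.9915 = 12.7%; placebo 1 − 0.95·0.983 = 6.6%; difference 6.1 points.
- f=50%: drug 1 − 0.88·0.9575 = 15.7%; placebo 1 − 0.95·0.915 = 13.1%; difference 2.7 points.

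Against 7.0 points with no background, the direction is toward hiding harm. The documents give no value for f, and none for ileus alone.

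**The case against.** A reader might infer that labor and surgical symptoms are charged to metronidazole as drug events. The documents do not support this. Section 7.14 lists event types, section 10 promises a summary of events that occurred, and neither attributes any event to the drug. The arms are randomized and blinded, so unrelated symptoms should fall on both. What remains is dilution.

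A reader might also infer that background symptoms swamp the comparison. That needs a background of roughly 20% or more, and the documents give no such rate. At 2% to 10% the loss is real but partial (70% to 44% power). At an 8% placebo rate power is only 31% even with a perfect window, so the window is not the only limit.

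The ileus overlap may be small. Ileus is one finding within one of five endometritis criteria, two of which are required, and it is one item in an open-ended list. The direction of the effect stands; its size is unknown.

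Finally, the 79% benchmark assumes that every dosing-period symptom is recorded. The plan adds no study visit and relies on the chart. If only half of the symptoms in each arm were captured (assumption: 6% versus 2.5%), power would be 48% with no background at all. That objection is correct: a window sorts recorded events and cannot recover unrecorded ones.

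**Conclusion.** The concern holds as a defect in how adverse events are counted. No onset window exists, observation falls mostly outside the exposure week, and the resulting count mixes peripartum symptoms with symptoms during dosing. The certain part is algebraic: a shared background b multiplies the risk difference by (1−b). The size is illustrative. With 12% against an assumed 5% and 241 per arm, power is 79%, 58%, 44% and 28% at b of 0, 5%, 10% and 20%. These figures rest on placebo and background rates that the documents do not give. The overlap of ileus with endometritis adds a possible bias toward hiding harm, of unknown and perhaps small size. The point concerns one secondary safety outcome and leaves the primary comparison and its sample size untouched.

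**What to change.** In section 7.14:

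- Make the main adverse-event comparison events with onset from the first dose to a fixed number of days after the last dose, for example 7. Apply the same rule to all women.
- Do not end the window at labor admission. Enrollment is open at any gestation from 34 weeks, so some women may labor during the course. A cut there would discard true on-drug events and end observation at a post-randomization event.
- Add an onset date to the adverse-event form.
- Tabulate later events separately by arm, so that nothing is lost.
- Show ileus adjudicated as part of a primary-outcome infection on its own line, and report the total both with and without it. Excluding it outright would condition the harm count on an outcome that treatment may change.

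The cost is protocol wording and one data field. Late-onset reactions move to a second table. The window does not recover dosing-week symptoms that were never recorded.
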